4.4 Benefit/Risk

Subjects in clinical trials generally cannot expect to receive direct benefit from treatment/vaccination during participation, as clinical trials are designed to provide information about the safety and effectiveness of an investigational medicine.

Additional details regarding specific benefits and risks for subjects participating in this clinical trial may be found in the accompanying Investigators Brochure (IB) and Informed Consent documents.

5.0 METHODOLOGY

5.1 Entry Criteria

5.1.1 Diagnosis/Condition for Entry into the Trial

Male and female subjects with newly diagnosed RCC at least 18 years of age will be enrolled in this trial.

5.1.2 Subject Inclusion Criteria

In order to be eligible for participation in this trial, the subject must:

1. Be willing and able to provide written informed consent/assent for the trial. The subject may also provide consent for Future Biomedical Research. However, the subject may participate in the main trial without participating in Future Biomedical Research.
2. Be ≥ 18 years of age on day of signing informed consent.
3. Have newly diagnosed RCC, with a primary tumor diameter of more than 4 cm ($\geq T1b$), not previously treated, and be a candidate for operative tumor resection.
4. Be willing and able to undergo pre-treatment baseline image-guided core biopsy of their primary RCC (unless a diagnostic biopsy has already been performed within 45 days prior to the first dose of MK-3475 and sufficient RCC tissue is available for study-related analyses).
5. Have a performance status of 0 or 1 on the ECOG Performance Scale.

6. Demonstrate adequate organ function as defined in [Table 1](#), based on screening labs.

Table 1 Adequate Organ Function Laboratory Values

| System | Laboratory Value |
|---|---|
| Hematological | |
| Absolute neutrophil count (ANC) | $\geq 1,500 / \text{mcL}$ |
| Platelets | $\geq 100,000 / \text{mcL}$ |
| Hemoglobin | $\geq 9 \text{ g/dL}$ or $\geq 5.6 \text{ mmol/L}$ |
| Renal | |
| Serum creatinine OR Measured or calculated ^a creatinine clearance (GFR can also be used in place of creatinine or CrCl) | $\leq 1.5 \times \text{ upper limit of normal (ULN)}$ OR $\geq 60 \text{ mL/min}$ for subject with creatinine levels $> 1.5 \times$ institutional ULN |
| Hepatic | |
| Serum total bilirubin | $\leq 1.5 \times \text{ ULN}$ OR Direct bilirubin $\leq \text{ ULN}$ for subjects with total bilirubin levels $> 1.5 \text{ ULN}$ |
| AST (SGOT) and ALT (SGPT) | $\leq 2.5 \times \text{ ULN}$ OR $< 5 \times \text{ ULN}$ for subjects with liver metastases |
| Coagulation | |
| International Normalized Ratio (INR) or Prothrombin Time (PT) | $\leq 1.5 \times \text{ ULN}$ |
| Activated Partial Thromboplastin Time (aPTT) | $\leq 1.5 \times \text{ ULN}$ |

^a Creatinine clearance should be calculated per institutional standard.

7. Be a male, or a non-pregnant and non-breast feeding female; further:

- if female with reproductive potential: subject must demonstrate a serum β -human chorionic gonadotropin (β -hCG) level consistent with the nongravid state at the screening visit and agree to use (and/or have their partner use) two (2) acceptable methods of birth control beginning at the screening visit, throughout the trial and until 120 days after the last dose of MK-3475 or until the last blood draw (for non-treatment controls). Acceptable methods of birth control are defined in Section 5.7.2.
- if postmenopausal female: subject is without menses for at least 1 year and have a documented follicle stimulating hormone (FSH) level in the postmenopausal range at screening,
- if a surgically sterile female: subject is status post hysterectomy, oophorectomy, or tubal ligation.

NOTE: These procedures must be confirmed with medical records. In the absence of documentation, hysterectomy may be confirmed by pelvic exam or if necessary by ultrasound; oophorectomy may be confirmed by hormone levels, particularly FSH in the post-menopausal range, but tubal ligation subjects without records should be excluded, unless they demonstrate a serum β -human chorionic gonadotropin (β -hCG) level consistent with the nongravid state at the screening visit and agree to use (and/or have their partner use) two (2) acceptable methods of birth control beginning at the screening visit, throughout the trial and until 120 days after the last dose of MK-3475 or until the last blood draw (for non-treatment controls). Information must be captured appropriately within the site's source documents

8. Male subjects with a female partner of childbearing potential should agree to use an adequate method of contraception starting with the first dose of study therapy through 120 days after the last dose of study therapy or until the last blood draw (for non-treatment controls). If their partner is pregnant, male subjects must agree to use a condom and no additional method of contraception is required for the pregnant partner. If their partner is of child-bearing potential, male subjects should use a condom with spermicide.

5.1.3 Subject Exclusion Criteria

The subject must be excluded from participating in the trial if the subject:

1. Is currently participating and receiving study therapy or has participated in a study of an investigational agent and received study therapy or used an investigational device within 4 weeks of screening.
2. Has a diagnosis of immunosuppression or has received systemic steroid therapy or any other form of immunosuppressive therapy within 4 weeks prior to screening.
3. Has had prior chemotherapy, targeted small molecule therapy, or radiation therapy for the treatment of RCC.
4. Has a known additional malignancy (other than RCC) that is progressing or requires active treatment. Exceptions include basal cell carcinoma of the skin, squamous cell carcinoma of the skin, and *in situ* cervical cancer that has undergone potentially curative therapy.
5. Has known active central nervous system (CNS) metastases and/or carcinomatous meningitis. The presence of RCC metastases to other sites is permitted.
6. Has an active autoimmune disease or a documented history of autoimmune disease. Subjects with vitiligo or resolved childhood asthma/atopy are an exception to this rule. Subjects that require intermittent use of bronchodilators will not be excluded from the study.
7. Has a history of (non-infectious) pneumonitis that required treatment with steroids or current pneumonitis.
8. Has an active infection requiring systemic therapy.

9. Is receiving anticoagulant therapy or has received anticoagulant therapy within 10 days prior to screening. Certain platelet aggregation inhibitors are permitted (see Section 5.5.1 below)
10. Has severe cardiovascular disease, i.e. arrhythmias, requiring chronic treatment, congestive heart failure (NYHA Class III or IV) or symptomatic ischemic heart disease.
11. Has hepatic decompensation (Child-Pugh score > 6 [class B and C]).
12. Has uncontrolled thyroid dysfunction. Subjects with hypothyroidism stable on thyroid hormone replacement will not be excluded from the study.
13. Has uncontrolled diabetes mellitus.
14. Has a history or current evidence of any condition, therapy, or laboratory abnormality that might confound the results of the trial, interfere with the subject's participation for the full duration of the trial, or is not in the best interest of the subject to participate, in the opinion of the treating investigator.
15. Has known psychiatric or substance abuse disorders that would interfere with cooperation with the requirements of the trial.
16. Is pregnant or breastfeeding, or expecting to conceive or father children within the projected maximal duration of the trial, which would extend from the screening visit through 120 days after the last dose of study drug of MK-3475 or until the last blood draw (for non-treatment controls).
17. Has received prior therapy with an anti-PD-1, anti-PD-L1, anti-PD-L2, anti-CD137, or anti-CTLA-4 antibody (including ipilimumab) or any other antibody or drug specifically targeting T-cell co-stimulation or checkpoint pathways.
18. Has a known history of Human Immunodeficiency Virus (HIV) (HIV 1/2 antibodies).
19. Has known active Hepatitis B (e.g., HBsAg reactive) or Hepatitis C (e.g., HCV RNA [qualitative] is detected).
20. Has received a live vaccine within 30 days prior to screening.

5.2 Trial Treatment(s)

The treatment to be used in this trial is outlined below in [Table 2](#).

Table 2 Trial Treatment

| Biologic | Dose/ Potency | Dose Frequency | Route of Administration | Regimen | Use |
|----------|------------------|-------------------|----------------------------|--------------------------|---------------------------------|
| MK-3475 | 200 mg | Q3 weeks | IV | 2 (or up to 3*) doses | Experimental, Neoadjuvant |
| MK-3475 | 200 mg | Q3 weeks | IV | Up to 17 doses† | Experimental, Post-Resection |

*Potential increase in number of doses will be based on interim analysis (see Section 8.0).
†MK-3475 doses may be withheld due to toxicity, as described in Section 5.2.1.2.

Trial Treatment should begin within 28 days of randomization or treatment assignment for those randomized to receive neoadjuvant MK-3475.

The investigator shall take responsibility for and shall take all steps to maintain appropriate records and ensure appropriate supply, storage, handling, distribution and usage of trial treatments in accordance with the protocol and any applicable laws and regulations.

5.2.1 Dose Selection/Modification

5.2.1.1 Dose Selection (Preparation)

For those subjects randomized to receive neoadjuvant treatment, MK-3475 (200 mg) will be administered intravenously Q3W for a total of two (or possibly three) doses. Two to three weeks following the final dose, patients should undergo SOC surgical resection of their RCC tumors.

Following recovery from surgical RCC resection, all subjects may receive MK-3475 (200 mg) administered intravenously Q3W for up to 17 doses (1 year of treatment).

The rationale for selection of doses to be used in this trial is provided in Section 4.0 – Background & Rationale. There are no specific calculations or evaluations required to be performed in order to administer the proper dose to each subject.

5.2.1.2 Dose Modification and Toxicity Management Guidelines for Pembrolizumab

Dose modification and toxicity management for immune-related AEs associated with pembrolizumab

AEs associated with pembrolizumab exposure may represent an immunologic etiology. These immune-related AEs (irAEs) may occur shortly after the first dose or several months after the last dose of pembrolizumab treatment and may affect more than one body system simultaneously. Therefore, early recognition and initiation of treatment is critical to reduce complications. Based on existing clinical trial data, most irAEs were reversible and could be managed with interruptions of pembrolizumab, administration of corticosteroids and/or other supportive care. For suspected irAEs, ensure adequate evaluation to confirm etiology or exclude other causes. Additional procedures or tests such as bronchoscopy, endoscopy, skin biopsy may be included as part of the evaluation. Based on the severity of irAEs, withhold or permanently discontinue pembrolizumab and administer corticosteroids. Dose modification and toxicity management guidelines for irAEs associated with pembrolizumab are provided in [Table 6](#) for neoadjuvant dosing and [Table 3](#) for post-resection dosing.

5.2.1.2.1.1 Neoadjuvant MK-3475

Based on the first interim analysis of lymphocytic infiltrates in tumors resected from the first 9 subjects, if an increase in tumor lymphocytic infiltration of 2-fold or greater is not observed in more than one of the 6 subjects in this group that received a 2 dose course of neoadjuvant

MK-3475, all subsequent subjects enrolled in this trial may be treated with 3 doses of MK-3475. Details are described in Section 8.0 – Statistical Analysis Plan.

Administration of neoadjuvant MK-3475 during this trial must be discontinued for drug-related toxicities above Grade 1 in severity and for severe or life-threatening AEs as described in Section 5.6.1. Such subjects should proceed with SOC surgical RCC resection as soon as they have sufficiently recovered from the AE to undergo this procedure.

For subjects without metastatic disease at the time of surgical RCC resection who experience drug-related toxicities above Grade 1 during neoadjuvant treatment, post-resection MK-3475 should also not be administered and the subject should be permanently discontinued. However, subjects with known metastatic disease at the time of surgical RCC resection who develop Grade 2 or greater drug-related AEs during neoadjuvant MK-3475 treatment may still be eligible to receive post-resection MK-3475 if the drug-related AE severity as listed in [Table 3](#) below does not prescribe permanent treatment discontinuation.

5.2.1.2.1.2 Post-Resection MK-3475

Post-resection administration of MK-3475 must be withheld for drug-related toxicities and severe or life-threatening AEs as per [Table 3](#) below. See Section 5.6.2 for supportive care guidelines, including use of corticosteroids to be followed during post-resection administration of MK-3475 (only applicable in the Post-Resection Phase of the study).

Table 3 Dose Modification and Toxicity Management Guidelines for Immune-related AEs Associated with Pembrolizumab (During Post-Resection Phase ONLY)

| General instructions: | | | | |
|------------------------------|---|--------------------------------------|---|--|
| Immune-related AEs | Toxicity grade or conditions (CTCAEv4.0) | Action taken to pembrolizumab | irAE management with corticosteroid and/or other therapies | Monitor and follow-up |
| Pneumonitis | Grade 2 | Withhold | 
 Administer corticosteroids (initial dose of 1-2 mg/kg prednisone or equivalent) followed by taper | 
 Monitor participants for signs and symptoms of pneumonitis Evaluate participants with suspected pneumonitis with radiographic imaging and initiate corticosteroid treatment Add prophylactic antibiotics for opportunistic infections |
| | Grade 3 or 4, or recurrent Grade 2 | Permanently discontinue | | |
| Diarrhea / Colitis | Grade 2 or 3 | Withhold | 
 Administer corticosteroids (initial dose of 1-2 mg/kg prednisone or equivalent) followed by taper | 
 Monitor participants for signs and symptoms of enterocolitis (ie, diarrhea, abdominal pain, blood or mucus in stool with or without fever) and of bowel perforation (ie, peritoneal signs and ileus). Participants with \geq Grade 2 diarrhea suspecting colitis should consider GI consultation and performing endoscopy to rule out colitis. Participants with diarrhea/colitis should be advised to drink liberal quantities of clear fluids. If sufficient oral fluid intake is not feasible, fluid and electrolytes should be substituted via IV infusion. |
| | Grade 4 | Permanently discontinue | | |

| Immune-related AEs | Toxicity grade or conditions (CTCAEv4.0) | Action taken to pembrolizumab | irAE management with corticosteroid and/or other therapies | Monitor and follow-up |
|--|--|--|---|---|
| AST / ALT elevation or Increased bilirubin | Grade 2 | Withhold | 
 Administer corticosteroids (initial dose of 0.5- 1 mg/kg prednisone or equivalent) followed by taper | 
 Monitor with liver function tests (consider weekly or more frequently until liver enzyme value returned to baseline or is stable) |
| | Grade 3 or 4 | Permanently discontinue | 
 Administer corticosteroids (initial dose of 1-2 mg/kg prednisone or equivalent) followed by taper | |
| Type 1 diabetes mellitus (T1DM) or Hyperglycemia | Newly onset T1DM or Grade 3 or 4 hyperglycemia associated with evidence of β -cell failure | Withhold | 
 Initiate insulin replacement therapy for participants with T1DM Administer anti-hyperglycemic in participants with hyperglycemia | 
 Monitor participants for hyperglycemia or other signs and symptoms of diabetes. |
| Hypophysitis | Grade 2 | Withhold | 
 Administer corticosteroids and initiate hormonal replacements as clinically indicated. | 
 Monitor for signs and symptoms of hypophysitis (including hypopituitarism and adrenal insufficiency) |
| | Grade 3 or 4 | Withhold or permanently discontinue ¹ | | |
| Hyperthyroidism | Grade 2 | Continue | 
 Treat with non-selective beta-blockers (eg, propranolol) or thionamides as appropriate | 
 Monitor for signs and symptoms of thyroid disorders. |
| | Grade 3 or 4 | Withhold or permanently discontinue ¹ | | |
| Hypothyroidism | Grade 2-4 | Continue | 
 Initiate thyroid replacement hormones (eg, levothyroxine or liothyronine) per standard of care | 
 Monitor for signs and symptoms of thyroid disorders. |
| Nephritis and Renal dysfunction | Grade 2 | Withhold | 
 Administer corticosteroids (prednisone 1-2 mg/kg or equivalent) followed by taper. | 
 Monitor changes of renal function |
| | Grade 3 or 4 | Permanently discontinue | | |

| Immune-related AEs | Toxicity grade or conditions (CTCAEv4.0) | Action taken to pembrolizumab | irAE management with corticosteroid and/or other therapies | Monitor and follow-up |
|--|---|---|---|--|
| Myocarditis | Grade 1 or 2 | Withhold | 
 Based on severity of AE administer corticosteroids | 
 Ensure adequate evaluation to confirm etiology and/or exclude other causes |
| | Grade 3 or 4 | Permanently discontinue | | |
| All other immune-related AEs | Intolerable/persistent Grade 2 | Withhold | 
 Based on type and severity of AE administer corticosteroids | 
 Ensure adequate evaluation to confirm etiology and/or exclude other causes |
| | Grade 3 | Withhold or discontinue based on the type of event. Events that require discontinuation include and not limited to: Guillain-Barre Syndrome, encephalitis | | |
| | Grade 4 or recurrent Grade 3 | Permanently discontinue | | |
| 
1. Withhold or permanently discontinue pembrolizumab is at the discretion of the investigator or treating physician.
 
NOTE: For participants with Grade 3 or 4 immune-related endocrinopathy where withhold of pembrolizumab is required, pembrolizumab may be resumed when AE resolves to \leq Grade 2 and is controlled with hormonal replacement therapy or achieved metabolic control (in case of T1DM).
 | | | | |

5.2.2 Timing of Dose Administration

MK-3475 solution for intravenous administration will be prepared and dosed per the instructions outlined in the Pharmacy Manual.

MK-3475 will be administered as a 30 minute IV infusion every 3 weeks (Q3W). The study site(s) should make every effort to target infusion timing to be as close to 30 minutes as possible. However, given the variability of infusion pumps from site to site, a window of -5 minutes and +10 minutes is permitted (i.e., infusion time is 30 minutes: -5 min/+10 min).

Trial treatment should be administered following the schedule in Section 6.0 and after all procedures/assessments have been completed as detailed on the Trial Flow Chart (Section 6.0). Unless otherwise specified, trial treatment may be administered up to 3 days before or after the scheduled day of each cycle for administrative reasons.

All trial treatments will be administered on an outpatient basis.

5.2.3 Trial Blinding/Masking

This is an open-label trial; therefore, the Sponsor, investigator and subject will know the treatment administered.

5.3 Randomization or Treatment Allocation

Subjects will be assigned randomly according to a computer-generated allocation schedule.

The sample allocation schedule is shown in [Table 4](#).

Table 4 Sample Allocation Schedule

| Patients ^a | Treatment Group |
|-----------------------|--|
| n=24 | 200 mg MK-3475 Q3 weeks, 2 or 3 doses ^b |
| n=12 | Control |

^a Patients will be randomized to receive neoadjuvant MK-3475 or control. Allocation will be done in blocks of 3, ensuring 6 treated and 3 controls will be available for the first interim analysis. Depending on results of the first interim analysis, the control arm (and allocation numbers associated with the control arm) may be dropped from the allocation schedule, in which case patient numbers will be 33 and 3 for MK-3475 and controls, respectively.

^b Also depending on the results of the first interim analysis, the number of neoadjuvant doses of MK-3475 may be increased from 2 to 3.

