2.0 TRIAL DESIGN

2.1 Trial Design

This is a Phase I, randomized, no treatment controlled trial of neoadjuvant administration of MK-3475 (also known as pembrolizumab) in subjects with newly diagnosed RCC, $\geq T1b$ (>4 cm diameter), to be conducted in conformance with Good Clinical Practices. Initially, subjects will be randomized 2:1 to receive either neoadjuvant MK-3475 or serve as untreated controls. Those to receive neoadjuvant MK-3475 will undergo image-guided core needle biopsy of their tumor with collection of a minimum of three cores of tumor tissue. Tissue from this block will be used by the local pathologist to confirm the diagnosis of RCC prior to the administration of MK-3475, and remaining tissue will be used for study analyses. Blood and urine samples for biomarker analysis will also be collected at the time of core biopsy in patients randomized to receive neoadjuvant MK-3475. Two to 3 weeks after the final neoadjuvant dose of MK-3475 (administered at a dose of 200 mg IV Q3 weeks), additional blood and urine will be collected for biomarker analysis and patients will undergo SOC RCC surgical tumor resection. Control patients will proceed to surgery, without receiving neoadjuvant MK-3475, with the collection of blood and urine samples for biomarker analysis on the day of surgery. In the operating room, three or more core needle biopsy specimens of the RCC may be collected before tumor removal and prior to renal artery cross-clamping under direct vision, at the discretion of the operating surgeon and subject to local institutional review board approval. Upon surgical removal of the tumor, a minimum of 10 cm³ of non-necrotic resected tumor tissue will be collected and shipped as fresh tissue to Merck Research Laboratories for analyses. From the remaining resected tumor tissue, additional research samples will be collected for formalin fixation, snap freezing, and placement in RNAlater solution, while the remaining tumor tissue will be used by the local clinical site pathologist for routine clinical diagnostic purposes. Additional blood and urine samples for biomarker analyses will be collected from all subjects during post-operative follow up.

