Following recovery from surgery, each subject may receive post-resection MK-3475. During this phase of the trial, subjects should be evaluated by SOC radiologic imaging at intervals to be selected by their treating physicians. The physician should utilize RECIST 1.1 and/or irRECIST for making clinical management decisions. AEs should be monitored throughout the trial and graded in severity according to the guidelines outlined in the NCI Common Terminology Criteria for Adverse Events (CTCAE), version 4.0.

Treatment with post-resection MK-3475 may continue until documented disease progression or recurrence, unacceptable AE(s), intercurrent illness that prevents further administration of treatment, investigator's decision to withdraw the subject, consent withdrawn by subject, start of new anti-cancer treatment, subject is lost to follow up, pregnancy of the subject, noncompliance with trial treatment or procedure requirements, completion of 17 administrations of post-resection MK-3475 (approximately 1 year of treatment), or discontinuation for administrative reasons.

After the final study visit, routine SOC clinical follow up will continue. Since the majority of recurrences (83%) after surgical resection in RCC occur within 2 years of surgery [1], the clinical outcome will be queried for each subject 1 and 2 years following surgical tumor resection.

Specific procedures to be performed during the trial, as well as their prescribed times and associated visit windows, are outlined in the Trial Flow Chart - Section 6.0. Details of each procedure are provided in Section 7.0 – Trial Procedures.

This trial will use an adaptive design based on pre-specified criteria. There will be up to three formal interim analyses. The first interim analysis will be conducted after 9 subjects have entered the trial and the immune cell infiltrates in their surgically resected RCC specimens have been assessed. The second interim analysis will be conducted after 9 additional subjects have entered the trial and the immune cell infiltrates in their surgically resected RCC specimens have been assessed. The third interim analysis may be conducted when 9 additional subjects have entered the trial and the immune cell infiltrates in their surgically resected RCC specimens have been assessed. See section 8.0 – Statistical Analysis Plan, for additional details regarding sample size determination.

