5.4 Stratification

No stratification based on age, sex or other characteristics will be used in this trial.

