5.9 Subject Replacement Strategy

If a subject discontinues from the trial, a replacement subject may be enrolled if deemed appropriate by the investigator and Sponsor. The replacement subject will generally receive the same treatment or treatment sequence (as appropriate) as the subject being replaced. The replacement subject will be assigned a unique randomization number. The trial site should contact the Sponsor for the replacement subject's randomization number.

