The second interim analysis will occur after a total of 18 RCC patients have undergone tumor resection, with either 15 receiving neoadjuvant MK-3475 with 3 controls or 12 receiving neoadjuvant MK-3475 with 6 controls. The primary PD hypothesis will be assessed, and success will be declared and enrollment may stop if there is at least 80% posterior probability that the true response rate is at least 30%. If success cannot be declared after the initial 18

patients, an additional 9 patients may be enrolled and randomized as determined by the results of the first interim analysis, and a third interim analysis will occur after 27 RCC patients have undergone tumor resection, with either 24 receiving neoadjuvant MK-3475 with 3 controls or 18 receiving neoadjuvant MK-3475 with 9 controls. The primary hypothesis will be assessed, and success will be declared and enrollment may stop if there is at least 70% posterior probability that the true response rate is at least 30%. If success cannot be declared after the initial 27 patients, an additional 9 patients may be enrolled and randomized as determined by the results of the first interim analysis. The final analysis will be performed after 36 RCC patients have undergone tumor resection. At the final analysis, success will be declared if there is at least 60% posterior probability that the true response rate is at least 30%.

After each interim analysis, decisions related to enrolling additional patients may deviate from the rules defined above based on the accumulating data, at the discretion of the Sponsor.

In addition, decisions related to stopping the study for futility may also be considered at each interim analysis. At the second interim analysis, if there are only 0 or 1 responders the study may be stopped for futility. The probability of this happening when the true response rate is 30% is 8.5% (3.5%) with a sample size of 12 (15). At the third interim analysis, if there are 2 or less responders the study may be stopped for futility. The probability of this happening when the true response rate is 30% is 6.0% (1.2%) with a sample size of 18 (24).

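### Table 4 discloses a fixed block of 3 in an open-label trial; one 6:3 block of 9 per interim cohort would roughly halve the assignments that can be known in advance, though the practical effect is modest.

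*Combined protocol and SAP*

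**What the plan says.** - **Ratio.** Section 2.1: "Initially, subjects will be randomized 2:1 to receive either neoadjuvant MK-3475 or serve as untreated controls".
- **Block size.** Section 5.3, Table 4 footnote a: "Allocation will be done in blocks of 3, ensuring 6 treated and 3 controls will be available for the first interim analysis". This is the only block size given and the only reason given for it. Nothing in the documents varies the block size or withholds it from sites.
- **Masking.** Section 5.2.3: "This is an open-label trial; therefore, the Sponsor, investigator and subject will know the treatment administered".
- **Stratification.** Section 5.4: "No stratification based on age, sex or other characteristics will be used in this trial".
- **Replacements.** Section 5.9: "The replacement subject will generally receive the same treatment or treatment sequence (as appropriate) as the subject being replaced".
- **Looks.** Section 2.1 places the first interim analysis after 9 patients and the second after 9 more. Section 8.2.6 gives the arm sizes at the second look, "with either 15 receiving neoadjuvant MK-3475 with 3 controls or 12 receiving neoadjuvant MK-3475 with 6 controls", then 24:3 or 18:9 at 27 patients. Table 4 gives 24 and 12 at 36 patients, or 33 and 3 if the control arm is dropped.

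**The concern.** A 2:1 block of 3 has only three possible orders. Anyone who knows the block size and has seen the earlier assignments knows the third assignment of every block, and the second as well when the control comes first. Knowing the next arm before a patient is randomised opens a route to selection.

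The protocol leaves some room for this. Section 6.1 (footnote a) allows randomisation at any time between screening and biopsy. Exclusion 14 in Section 5.1.3 rests partly on the investigator's opinion. Section 4.2.2.4 acknowledges that the delay before surgery may worry patients and physicians. Patients with and without metastatic disease are both eligible.

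Two things are at stake. One is the make-up of the MK-3475 group, including the 6 patients whose responses decide at the first interim analysis whether controls continue and whether the number of doses may rise. The other is any comparison with concurrent controls.

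**Working it through.** **Inputs.** Block of 3 and 2:1 ratio (Sections 5.3 and 2.1); open-label and unstratified (5.2.3 and 5.4); cohorts of 9 (2.1 and 8.2.6). The documents state no predictability figure.

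**The plan's own arm sizes reproduce.** Three blocks of 2+1 give 6:3 and twelve give 24:12. Dropping controls after the first 9 gives 6 + 27 = 33 treated and 3 controls.

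**Assignments known with certainty.** An assignment is forced once only one arm is left in the block. With T treated and C control places and all orders equally likely, the expected number forced is T/(C+1) + C/(T+1). Enumerating every order gives the same values.

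- Block of 3 (T=2, C=1): the orders TTC, TCT and CTT leave 1, 1 and 2 forced. The mean is 2/2 + 1/3 = 1.333 of 3 = 44.4%. That is 4.0 of the first 9, or 16 of 36 if 2:1 randomisation runs throughout.
- Block of 9 (T=6, C=3; 84 orders): 6/4 + 3/7 = 1.929 of 9 = 21.4%. That is 1.9 of the first 9, or 7.7 of 36.

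The first term counts forced MK-3475 places. In the first cohort these are 3 × 1 = 3 of 6 with blocks of 3, and 1.5 of 6 with a block of 9.

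**Best-guess accuracy.** The observer always names the arm with more places left, and a tie counts one half.

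| Strategy | Correct |
|---|---|
| Always name MK-3475 | 66.7% |
| Block of 3 | 77.8% |
| Block of 9 | 72.8% |

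For the block of 3, the three positions are right with probability 2/3, 1/3 + (2/3)(1/2) = 2/3, and 1; the mean is 77.8%. The block-of-9 figure comes from enumerating the 84 orders.

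**Arm sizes with blocks of 9.** 6:3, 12:6, 18:9 and 24:12 at 9, 18, 27 and 36 patients. These match Section 8.2.6 and Table 4. Dropping controls after a completed cohort of 9 still gives 33:3.

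**How long the issue lasts.** Under Section 8.2.6, controls may be dropped if fewer than 4 of the first 6 treated patients respond. At a true rate of 30% the binomial probability of 4 or more is 7.0%, as Table 12 prints, so fewer than 4 has probability 93%. At 40% it is 1 − (0.1382 + 0.0369 + 0.0041) = 82%. On that path block size matters only for the first 9 patients: 4.0 against 1.9 certain assignments, a difference of about two patients.

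**The case against.** A reader might infer that 44% of assignments are in fact known to the staff who enrol patients. The documents do not support that. The figure needs sight of every earlier assignment in the block. Section 5.2.2 refers to infusion pumps differing between sites, which points to more than one site, and the number of sites is not stated. On a single central list, staff at one site see only part of the sequence.

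A reader might also infer that a replacement's arm is always known. Section 5.9 says only that this is generally so, and as appropriate. Changing the block size does nothing about it.

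The harm is also limited by the analysis. Section 8.2.4 tests the treated-arm response rate against 30% with no control comparison. It contrasts surgical complications with published rates because within-study comparison would lack power. The control comparison visible there is optional and depends on control enrolment continuing; redacted text may hold others. No size or direction of bias in the 30% comparison can be shown.

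The remedy has limits too. Best-guess accuracy improves by only five points. Deleting the block size conceals little, because the printed looks and splits let a reader infer a 6:3 block of 9; the 21% already assumes the reader knows it. A block of 9 also allows six treated patients followed by three controls, so balance over time within a cohort is looser than with blocks of 3.

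All of this stands as a limit on size. None of it supplies a need for blocks of 3, since the stated purpose of 6 treated and 3 controls at the first look is met equally well by a block of 9.

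**Conclusion.** The point holds as a design weakness of modest effect. For an observer with full sight of earlier assignments, the disclosed block of 3 makes an expected 44% of assignments certain while 2:1 randomisation runs, against 21% with one 6:3 block per cohort. The 44% applies in full to the Sponsor, to a single site, or to sites that share information; it is a ceiling for one of several sites.

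It would go too far to conclude that the primary result is biased. The documents show a route, through the make-up of the MK-3475 arm and any optional control comparison, but no magnitude. If fewer than 4 of 6 respond and the option to drop controls is taken, the issue is confined to the first 9 patients. Those 9 still matter, because the 6 treated patients among them drive the adaptation and one patient can move the responder count across a threshold.

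**What to change.** For each interim cohort not yet allocated, generate the schedule as one random block of 9 with 6 MK-3475 and 3 control places. Remove the block size from Table 4 footnote a, keep the commitment to 6 and 3 at the first look, and hold the block structure in the randomisation file.

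The cost is a new allocation list and a footnote edit. Sample size, arm sizes at the planned looks and the option to drop controls are unchanged. The 6:3 split is guaranteed only at completed cohorts of 9, which is when the analyses are planned, and the looser balance within each cohort is a small price. Cohorts already allocated gain nothing, and the predictability of replacement subjects under Section 5.9 remains as it is.
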